2.6.4.2 Vital signs

Vital signs will include the collection of weight (kg), body temperature (recorded in °C), supine systolic and diastolic blood pressure (mmHg) and pulse (beats/min) measurements with the possibility of repeated vital assessments.

All vital signs data will be listed by treatment group, participant, and visit/time and if ranges are available, abnormalities (and relevant orthostatic changes) will be flagged. Summary statistics will be provided by treatment and visit/time.

A listing of all newly occurring or worsening abnormalities as compared with baseline will be provided, as well as a by-participant listing of all vital signs.

2.7 Pharmacokinetic endpoints

Not Applicable

2.8 PD and PK/PD analyses

Exploratory longitudinal PD modeling may be performed to identify potential relationships for safety, clinical and parasitological endpoints.

2.9 Participant-reported outcomes

Not Applicable

Commercially Confidential Information

2.11 Other Exploratory analyses (PD analysis set)

2.12 Interim analysis

3 Sample size calculation

3.1 Primary endpoint(s)

Approximately 10 participants in each cohort will be enrolled to receive ABO809. The sample size is driven by clinical trial site capacity.

The calculation is based on the 1-sided 80% exact confidence interval.

3.2 Secondary endpoint(s)

Commercially Confidential Information

The calculation is based

on the 1-sided 80% exact confidence interval.

4 Change to protocol specified analyses

None

5 Appendix

5.1 Imputation rules

5.1.1 Study treatment

The study treatment administration date should be complete since it is taken at the clinic. In case missing or partial, the visit date will be used as the study treatment administration date.

5.1.2 AE date imputation

The following missing dates will not be imputed:

- Missing AE start dates
- AE start dates missing the year
- Partial/missing AE end dates

For other type of partial missing start dates, rules specified in Table 5-1 to Table 5-3 will be used.

Table 5-1 AE/Treatment Date Abbreviations

	Day	Month	Year
Partial Adverse Event Start Date	<not used=""></not>	AEM	AEY
Treatment Start Date (TRTSTD)	<not used=""></not>	TRTM	TRTY

Table 5-2 describes the possible combinations and their associated imputations. The upper text indicates the imputation (NC, A, B, C, etc.) and the lower text the relationship of the AE start date to the treatment start date (TRTSTD).

Table 5-2	Imputation algorithm
-----------	----------------------

	AEM MISSING	AEM < TRTM	AEM = TRTM	AEM > TRTM
AEY MISSING	NC	NC	NC	NC
	Uncertain	Uncertain	Uncertain	Uncertain
AEY < TRTY	(D)	(C)	(C)	(C)
	Before TRTSTD	Before TRTSTD	Before TRTSTD	Before TRTSTD
AEY = TRTY	(B)	(C)	(B)	(A)
	Uncertain	Before TRTSTD	Uncertain	After TRTSTD
AEY > TRTY	(E)	(A)	(A)	(A)
	After TRTSTD	After TRTSTD	After TRTSTD	After TRTSTD

The legend to the above table is shown in Table 5-3.

Table 5-3 Imputation algorithm legends

		_
Relationship		
	Before TRTSTD	Indicates AE start date prior to Treatment Start Date
	After TRTSTD	Indicates AE start date after Treatment Start Date
	Uncertain	Insufficient to determine the relationship of AE start date to Treatment Start Date
Imputation		
calculation	NC/Blank	No convention/imputation
	(A)	01MONYYYY
	(B)	TRTSTD+1
	(C)	15MONYYYY
	(D)	01JULYYYY
	(E)	01JANYYYY

5.1.3 Concomitant medication date imputation

Missing concomitant dates will be imputed similar as to AE dates.

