	Commercially Confidential Informat	tion	
Occult Blood			
Cryptosporidium Antigen by EIA ^{10, 12}			

Period	Post-Study Follow-Up		
Visit Name	Post-Study Follow-Up Call		
Days	6 Month Phone Contact Commercially Confidential Information	12 Month Phone Contact on	
lgA			
	Commercially Confidential Informa	tion	
Evaluation of Clinical Signs and Symptoms ⁶			
CHIM Diary			
Standard of Care Drug Administration (Nitazoxanide) ⁸			
Concomitant medications			
Adverse Events	S ¹⁵	S ¹⁵	
•	Commercially Confidential Information	on	
Safety Follow-Up Call for Study Participants	S	s	
Study completion information			

Commercially Confidential Information

² Serum pregnancy tests at Screening and Day 28. Urine pregnancy test at Baseline.

³ Before ABO809 administration.

⁴ Participants should make every attempt to bring self-collected stool specimen to the clinic for each Outpatient Follow-Up visit. In the 24 hours prior to each Outpatient Follow-Up visit, all stools should be collected.

⁵ During screening, the first diarrheal stool, and the first diarrheal stool with relapse after clinical clearance will be tested for enteral pathogenic micro-organisms.

⁶ Includes number and frequency of diarrheal episodes, stool weight, volume, and grading (see Section 8.3.2, Section 8.4.1, and Appendix 1). Additionally, includes evaluation of nausea, vomiting, abdominal pain or discomfort, abdominal tenderness, abdominal rebound, abdominal distension, fecal urgency, diarrhea, flatulence, tenesmus, poor appetite, dehydration, fever, and electrolyte imbalance

⁸ Nitazoxanide to be administered per Prescribing Information (i.e. 500 mg every 12 hours for 3 days). Nitazoxanide administration will be captured on the standard concomitant medication page, and no specific CRF is required.

Page **50** of **81** Protocol No. CABO809A02101

Period	Post-Study Follow-Up	
Visit Name	Post-Study Follow-Up Call	
Days	6 Month Phone Contact	12 Month Phone Contact

¹¹ Additional tests can be done at the discretion of the Investigator e.g., in the case of dehydration.

Commercially Confidential Information

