2.3.4 Prior, concomitant and post therapies

Prior and concomitant medications will be coded according to the latest version of World Health Organization (WHO) Drug Reference List dictionary which employs the Anatomical Therapeutic Chemical (ATC). The number and percentage of participants taking prior and concomitant medications may be tabulated for each treatment by ATC class and PT. Concomitant rescue and other medications, procedures, and significant non-drug therapies may also be summarized by ABO809 treatment group and cohort number.

Prior medications are defined as drugs taken and stopped prior to first dose of study medication. Any medication given at least once between the day of first dose of study medication and the last day of study visit will be a concomitant medication, including those which were started before dosing and continued into the treatment period.

Rescue medication nitazoxanide

To minimize the risk of severe clinical illness, long-term asymptomatic shedding and recurrence of *Cryptosporidium* infection, nitazoxanide will be administered on Day 21 to all participants who receive ABO809 and develop a *Cryptosporidium* infection, whether or not clinical symptoms are observed.

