2.5.3 Handling of intercurrent events

Stool data with grade <3 will be set to missing after the participant took the rescue medication. For "Number of days of ...", "Duration of ...", "Stool output (weight)" variables, data will be right censored if the participant took the rescue medication. Proc Lifetest and Proc Lifereg will be used to calculate the median and mean (SE), respectively. If there are convergence issues with Proc Lifereg for some visits such as those starting on Day 21 when most measurements are censored then Proc Means will be used instead.

For all Kaplan-Meier graphs, participants will be censored under the following circumstances:

- If the study ended before the subject experienced the event.
- If the subject discontinued the study before experiencing the event.
- If the subject died before experiencing the event.
- If the subject took the rescue medication before experiencing the event.

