5.1.3.1 Prior therapies date imputation

Start date: The same rule which is applied to the imputation of AE/concomitant medication start date will be used.

End date:

- Imputed date = min (reference end date, DEC 31 of the year), if month and day are missing.
- Imputed date = min (reference end date, last day of the Month), if day is missing. where reference end date will be study informed consent date.

If the end date is not missing and the imputed start date is after the end date, use the end date as the imputed start date. If both the start date and the end date are imputed and if the imputed start date is after the imputed end date, use the imputed end date as the imputation for the start date.

Post therapies date imputation 5.1.3.2

Start date:

- If Day is missing, then impute to the max (reference start date, first day of the month).
- Day and month are missing then impute to the max (reference start date, Jan 1)
- Reference start date will be last date of study treatment administration + 1.

End date: No imputation

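### A nitazoxanide start recorded without its day can be imputed to as early as Study Day 2, and a partly dated AE that ended before dosing can be given an onset after its own end

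*SAP*

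**What the plan says.** **Where nitazoxanide is recorded.** Protocol Table 8-1, footnote 8: "Nitazoxanide administration will be captured on the standard concomitant medication page, and no specific CRF is required". Footnote 14 of that table confirms this and adds that diary contents are not entered on the diary eCRF page.

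**How a partial start is completed.** SAP 5.1.3: "Missing concomitant dates will be imputed similar as to AE dates". The AE rules in SAP Tables 5-2 and 5-3 give:
- start month equal to the dosing month, or month missing in the dosing year: dosing date + 1 (rule B);
- later month: first of that month (rule A);
- earlier month: the 15th of that month (rule C), which stays before dosing;
- start wholly missing, or year missing: no imputation.

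SAP 5.1.2 also leaves "Partial/missing AE end dates" unimputed. It has no rule for an imputed start that falls after a recorded end. SAP 5.1.3.1 has one, for prior therapies: "If the end date is not missing and the imputed start date is after the end date, use the end date".

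**When nitazoxanide is planned.** SAP 2.3.4: "nitazoxanide will be administered on Day 21 to all participants who receive ABO809 and develop a" *Cryptosporidium* infection. The same section allows a start once the Day 17 EIA result is available, a Day 10 start for persisting diarrhea, and a start at any time for severe illness.

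**What the rescue date controls.** SAP 2.5.3 censors Kaplan-Meier times "If the subject took the rescue medication before experiencing the event", right-censors the day-count, duration and stool-weight variables at rescue, and sets later stools of grade below 3 to missing. SAP 2.4.3 sets later negative infection results to missing in the time profiles.

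**The concern.** Dating an uncertain event just after dosing is a common cautious default for AE counting. It does not suit a drug whose start date is itself an intercurrent event and which is mostly planned about three weeks after dosing. Protocol 4.1 cites a median incubation of 3 to 11 days to diarrhea onset. Rescue imputed to Day 2 would usually censor a participant before an onset that was in fact observed.

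The participants exposed are not a random subset, because nitazoxanide is planned for everyone who becomes infected. The records at risk are those with events. Dropping negative results while keeping positive ones also pushes by-visit positivity upward. A cohort has about 10 participants and a dose group up to about 30, so one misdated record is 1/10 to 1/30 (10% to 3.3%) of the curve.

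On the AE side, an event that was over before ABO809 was given could be tabulated as occurring after it, with an onset later than its recorded end.

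**Working it through.** The plan states no figure here, so there is none to reproduce. The size follows from Tables 5-2 and 5-3.

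**Inputs.** Dosing is Day 1, so dosing date + 1 is Day 2 (SAP 2.1.1). The planned nitazoxanide start is Day 21, or Day 10 in the persisting-diarrhea case (SAP 2.3.4). Assumption: dosing dates spread evenly over a 365-day year (2022 was used).

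**Nitazoxanide, only the day missing, true start on Day D.**
- Rule A applies when the start falls in a later month than dosing. This holds for 12 × (D − 1) dosing dates. The shift is 0 to D − 2 days, each value occurring 12 times, with mean (D − 2)/2.
- Rule B applies on the other 365 − 12 × (D − 1) dates. The shift is always D − 2.

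| True start | Rule B dates | Rule A dates | Maximum shift | Mean shift |
|---|---|---|---|---|
| Day 10 | 257 | 108 | 8 | (257×8 + 108×4)/365 = 6.8 |
| Day 17 | 173 | 192 | 15 | (173×15 + 192×7.5)/365 = 11.1 |
| Day 21 | 125 | 240 | 19 | (125×19 + 240×9.5)/365 = 12.8 |
| Day 28 | 41 | 324 | 26 | (41×26 + 324×13)/365 = 14.5 |

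For a true Day 21 start:
- imputed to Day 2: 125 + 12 = 137 of 365 dates (38%); the extra 12 are month-end dosing dates reached through rule A;
- imputed to Day 10 or earlier: 125 + 9 × 12 = 233 of 365 (64%);
- too early by any amount: 365 − 12 = 353 of 365 (97%);
- mean imputed day: 21 − 12.75 = 8.25.

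If the month is missing as well, the mean shift is (345×19 + 20×9.5)/365 = 18.5 days.

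Example: dosing on 10 March, nitazoxanide on 30 March (Day 21), recorded as March. The imputed start is 11 March, Day 2.

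**Other rules in the SAP do not rescue this.** The post-therapy rule in SAP 5.1.3.2 takes the later of the first of the month and a reference date: "Reference start date will be last date of study treatment administration + 1". It gives the same dates on all 365 dosing dates. The end-date check of 5.1.3.1 would not help either, because the imputed start already lies before the end of the course.

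**AEs, only the day missing, true start s days before dosing.** Rule B applies on 365 − 12s dosing dates. Summed over s = 1 to 28: 28×365 − 12×406 = 5,348 of 10,220 combinations (52%) go to Day 2. The other 4,872 (48%) go to the 15th of the earlier month and stay pre-dose. For s = 1 to 7, 2,219 of 2,555 (87%) go to Day 2. Only those with a known end date before dosing are demonstrably wrong. Example: dosing on 10 March, AE from 4 to 6 March with the start day missing. The imputed onset is 11 March, five days after the event ended.

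**The case against.** The strongest objection is that the trigger is unlikely. The study is single-centre, nitazoxanide has its own entry in the Day 21 column of Table 8-1, and a Day 10 start falls while participants are domiciled. Protocol 4.1 has compliance recorded in a diary, Protocol 11.2 has missing values queried, and Protocol 11.3 requires full source verification of data for primary and secondary objectives. SAP 2.3.4 also foresees a check that doses were taken on successive days, which needs day-level dates. All of this stands: the percentages above are conditional on a missing day, and the documents give no rate of partial dates.

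A second objection is that SAP 5.1.3 asks for similar, not identical, treatment, and that SAP 5.1.1 already uses the visit date for product given in clinic. But 5.1.1 covers study treatment, a term SAP 2.1.1 reserves for ABO809, calling nitazoxanide rescue medication. As written, the AE algorithm is the only stated rule for its date.

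A third is that Table 5-2 labels the same-month AE case uncertain, and counting such events as post-dose avoids under-reporting. That is reasonable when the end date is unknown. It is no defence when a recorded end date shows the event finished before dosing.

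It is also unclear whether pre-dose AEs are captured at all. Protocol Section 10 and SAP 2.6.1 record AEs from Day 1, while Protocol 10.1.1 defines them from consent and Table 8-1 marks them at Screening and Baseline.

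**Conclusion.** The point holds as a narrow defect: a stated rule produces a wrong date in identifiable cases. A month-only nitazoxanide start is dated up to 19 days early for a true Day 21 start and up to 8 for a Day 10 start. The effect falls on the Kaplan-Meier, duration and stool summaries and the by-visit EIA profiles. An AE with a known pre-dose end, and a start recorded only to the dosing month or dosing year, receives an onset after its end and after dosing, provided such AEs are in the database.

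A reader might infer more than the documents support:
- **That every partial date moves past dosing.** Earlier-month starts go to the 15th and stay pre-dose, wholly missing starts are not imputed, and prior therapies have an end-date check.
- **That the primary result is biased.** SAP 2.4.3 removes only negative results, and only in the time profiles. Positive results up to Day 10 are kept, so the primary proportion does not change.
- **That 38%, 64% or 97% of participants would be misdated.** These are shares of dosing dates, given that the day is missing.

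Because partial dates should be rare, this is worth correcting but of low priority. The figures rest on evenly spread dosing dates; the 19- and 8-day maxima do not.

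**What to change.** 1. **SAP 5.1.3.** Exempt nitazoxanide from the AE algorithm. Following the convention of 5.1.1, complete a partial start with the date of the visit at which it was documented as given or dispensed, from source or diary. Do not use dosing + 1, and do not default to Day 21 when an earlier start is documented, for example one prompted by the Day 17 result. The shift is then 0 if treatment began at that visit.
2. **SAP 5.1.2.** Add the 5.1.3.1 rule: when the imputed AE start falls after a known end date, the end date becomes the start. No AE with a known pre-dose end can then be moved past dosing.
3. **Reconcile** Protocol Section 10 and SAP 2.6.1 with Protocol 10.1.1 and Table 8-1 on whether pre-dose AEs are recorded, since this decides whether item 2 has any effect.

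Items 1 and 2 cost two sentences in the SAP and a small programming change. Item 3 needs a short clarification. No new data collection is needed.

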5.1.3.1 Prior therapies date imputation

Start date: The same rule which is applied to the imputation of AE/concomitant medication start date will be used.

End date:

- Imputed date = min (reference end date, DEC 31 of the year), if month and day are missing.
- Imputed date = min (reference end date, last day of the Month), if day is missing. where reference end date will be study informed consent date.

If the end date is not missing and the imputed start date is after the end date, use the end date as the imputed start date. If both the start date and the end date are imputed and if the imputed start date is after the imputed end date, use the imputed end date as the imputation for the start date.

Post therapies date imputation 5.1.3.2

Start date:

- If Day is missing, then impute to the max (reference start date, first day of the month).
- Day and month are missing then impute to the max (reference start date, Jan 1)
- Reference start date will be last date of study treatment administration + 1.

End date: No imputation

5.1.3.3 Other imputations

N/A

5.2 **Prohibited medications**

Table 5-4 Table of prohibited medication with respective ATC codes

Prohibited medication	ATC code	ATC name
Antiperistaltic, antidiarrheal agents or	A02BX22	Bismuth subsalicylate
stool softeners	A03BA01	Atropine
	A07DA01	Diphenoxylate
	A07DA03	Loperamide
	H01CB02	Octreotide
	A07DA02	Opium tincture
	C10AC01	Cholestyramine
	C10AC02	Colestipol
	A06AA02	Docusate sodium
	A06AD11	Lactulose
Antithrombotic agents and other	B01AA03	Warfarin
agents prolonging QTc interval		
Antibacterial agents and other anti-parasitic therapies	A07AA06	Paromomycin alone or in combination with azithromycin
Yogurt, kefir, probiotics	N/A	N/A
vaccinations	N/A	N/A

AEs coding/grading 5.3

Grading will be assessed using the U.S. Food and Drug Administration's (FDA) "Toxicity Grading Scale for Healthy Adult and Adolescent Volunteers Enrolled in Preventive Vaccine Clinical Trials (2007)". For AE reporting based on laboratory values, local laboratory normal ranges may be used at the discretion of the Investigator, and if so, must be used consistently throughout the study. These may differ from the normal ranges given in the FDA grading scale. In case of such discrepancies, the Investigator will take into consideration the FDA recommendations as to the magnitude of deviations from normal provided in the FDA grading scale.

For AEs that are not contained in the "Toxicity Grading Scale for Healthy Adult and Adolescent Volunteers Enrolled in Preventive Vaccine Clinical Trials (2007)" the following categorization will be used:

- Mild: usually transient in nature and generally not interfering with normal activities
- Moderate: sufficiently discomforting to interfere with normal activities
- Severe: prevents normal activities

Stools will be graded according to this Stool Grading System by the Investigator. Grades 1 and 2 are considered normal stool and Grades 3-5 are considered diarrheal stool.

Table 5-5 Stool Grading System

Clinical Stool Classification	Stool Grade	Stool Description
Normal stool	1	Formed stool which does not take the shape of the container
Normal stool	2	Soft stool which does not easily take the shape of the container
Diarrheal stool	3	Thick liquid stool which does take the shape of the container
Diarrheal stool	4	Opaque watery stool
Diarrheal stool	5	Rice water stool, clear watery stool

Levine et al 1988, Sack et al 1998, Tribble et al 2009

